2.7.2 Statistical hypothesis, model, and method of analysis

PFS

The survival distribution of PFS will be estimated using the Kaplan-Meier method. The results will be plotted graphically (Kaplan-Meier curves) by cohort. The plots will display the number of patients at risk at equidistant time points. The median, 25th and 75th percentiles for PFS for each cohort will be provided with associated 95% confidence intervals ([Brookmeyer and Crowley 1982](#)). The survival probabilities at 6, 12, 18 months, and the associated 95% confidence intervals will be summarized by cohort. Kaplan-Meier estimates will be obtained using PROC LIFETEST with method=KM option in SAS. The loglog option available within PROC LIFETEST will be used to compute the confidence intervals.

ORR and CBR

ORR and CBR will be calculated based on the mFAS. ORR and CBR will be summarized using descriptive statistics (N, %) separately for each cohort along with two-sided exact binomial 95% CIs [Clopper and Pearson 1934]. As sensitivity analysis, CBR will be calculated and summarized for patients with only measurable disease at baseline.

Duration of Response

DOOR will be listed and summarized by cohort for all patients in the mFAS with confirmed BOR of CR or PR. The distribution of time to response will be estimated using the Kaplan-Meier method and the median time to response will be presented along with 95% confidence interval only if a sufficient number of responses is observed. A responders-only analysis will also be performed in this case.

OS

OS will be analyzed in the mFAS population. The distribution of OS will be estimated using the Kaplan-Meier method. The median OS along with 95% confidence intervals will be presented for each cohort.

PFS2

PFS2 will be analyzed in the mFAS population. The PFS2 distribution will be estimated using the Kaplan-Meier method, and the Kaplan-Meier curves, medians and 95% confidence intervals of the medians will be presented separately for each cohort.

Extension Phase Clinical Benefit

Proportion of patients with clinical benefit as assessed by the investigator will be summarized at scheduled visits. Clinical benefit will be summarized using the Safety Set in Extension Phase.

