1.2.5.2 Experience with alpelisib and fulvestrant in mBC

The combination of alpelisib with fulvestrant was investigated as part of study [CBYL719X2101] in 87 patients with heavily pre-treated HR+ mBC in two groups: patients with mutated PIK3CA (52 patients, 59.8%) and patients with wild-type PIK3CA (33 patients, 37.9%). For two patients (2.3%), PIK3CA mutational status was unknown. The MTD was declared at alpelisib 400 mg QD and fulvestrant 500mg q28 days, with DLTs in 4 patients (diarrhea, vomiting, decreased appetite, abdominal, distension and fatigue). Also alpelisib doses of 350 mg and 300 mg QD were investigated and mainly 300 mg QD emerged as the best tolerated dose in this combination. Overall, the most frequent AEs (>20%), regardless of grade, causality and alpelisib dose, suspected of being drug related were diarrhea (56.3%), nausea (42.5%), hyperglycemia (48.3%), decreased appetite (37.9%), fatigue (29.9%), vomiting (25.3%), stomatitis (27.6%) and fatigue (29.9%). Preliminary clinical efficacy of alpelisib + fulvestrant was demonstrated across all dose levels. Best overall response (BOR) achieved was confirmed PR for 13 (26.5%) patients and SD for 26 (53.1%) patients with PIK3CA mutant tumors versus PR for 0 (0%) patient and SD for 15 (46.9%) patients with PIK3CA non-mutant tumors. Disease control rate was 79.6% (95% CI: 65.7–89.8) and 46.9% (95% CI: 29.1–65.3) in the PIK3CA mutant and PIK3CA non-mutant groups, respectively. Estimated median PFS was longer in the PIK3CA mutant group vs PIK3CA non-mutant group (9.1 months vs 4.7 months). Overall, 7 patients are still on treatment in this study (2 on alpelisib as single agent, 5 receiving alpelisib with fulvestrant (Juric 2016). This data led to a design of phase III randomized, double-blind, placebo controlled study of alpelisib in combination with fulvestrant for men and postmenopausal women with hormone receptor positive, HER2-negative advanced breast cancer which progressed on or after aromatase inhibitor (AI) treatment [SOLAR-1, [CBYL719C2301].

For further details on clinical experience, please refer to the latest version of [Alpelisib Investigators Brochure].

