10.5.1.5 Duration of response

DOR is the time from the date of first documented response (confirmed CR or PR) to the date of first documented progression or death due to underlying cancer. DOR only applies to patients whose best overall response is CR or PR according to RECIST v1.1 based on tumor response data per local investigator's assessment. The start date is the date of first documented response of CR or PR (i.e., the start date of response, not the date when response was confirmed), and the end date is defined as the date of the first documented progression or death due to underlying cancer. Patients continuing without progression or death due to underlying cancer will be censored at the date of their last adequate tumor assessment.

DOR will be listed and summarized for each cohort in the mFAS with confirmed BOR of CR or PR. DOR will be summarized using Kaplan-Meier estimates in patients with confirmed CR or PR within each cohort.

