3.2.7 Time to response

Time to overall response (CR or PR) is the time between date of randomization/start of treatment until first documented response (CR or PR). The response may need to be confirmed depending on the type of study and its importance. Where the response needs to be confirmed then time to response is the time to the first CR or PR observed.

Although an analysis on the full population is preferred a descriptive analysis may be performed on the "responders" subset only, in which case the results should be interpreted with caution and in the context of the overall response rates, since the same kind of selection bias may be introduced as described for duration of response in Section 3.2.6. It is recommended that an analysis of all patients (both responders and non-responders) be performed whether or not a "responders only" descriptive analysis is presented. Where an inferential statistical comparison is required, then all patients should definitely be included in the analysis to ensure the statistical test is valid. For analysis including all patients, patients who did not achieve a response (which may have to be a confirmed response) will be censored using one of the following options.

- at maximum follow-up (i.e. FPFV to LPLV used for the analysis) for patients who had a PFS event (i.e. progressed or died due to any cause). In this case the PFS event is the worst possible outcome as it means the patient cannot subsequently respond. Since the statistical analysis usually makes use of the ranking of times to response it is sufficient to assign the worst possible censoring time which could be observed in the study which is equal to the maximum follow-up time (i.e. time from FPFV to LPLV)
- at last adequate tumor assessment date otherwise. In this case patients have not yet progressed so they theoretically still have a chance of responding

Time to overall complete response (CR) is the time between dates of randomization/start of treatment until first documented CR. Similar analysis considerations including (if appropriate) censoring rules apply for this endpoint described for the time to overall response endpoint.

Indicate in the protocol whether a subgroup analysis of responders only will be performed in addition to the full population analysis (which should be included as default).

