3.2.10 Sensitivity analyses

This section outlines the possible event and censoring dates for progression, as well as addresses the issues of missing tumor assessments during the study. For instance, if one or more assessment visits are missed prior to the progression event, to what date should the progression event be assigned? And should progression event be ignored if it occurred after a long period of a patient being lost to follow-up? It is important that the protocol and RAP specify the primary analysis in detail with respect to the definition of event and censoring dates and also include a description of one or more sensitivity analyses to be performed.

Based on definitions outlined in Section 3.2.8, and using the draft FDA guideline on endpoints (Clinical Trial Endpoints for the Approval of Cancer Drugs and Biologics, April 2005) as a reference, the following analyses can be considered:

Table 3-2 Options for event dates used in PFS, TTP, duration of response

		Options for end-date (progression or censoring) ¹ (1) = default unless specified differently in the protocol or RAP	Outcome
Α	No baseline assessment	(1) Date of randomization/start of treatment ³	Censored
В	Progression at or before next scheduled assessment	 (1) Date of progression (2) Date of next scheduled assessment² 	Progressed Progressed
C1	Progression or death after exactly one missing assessment	 (1) Date of progression (or death) (2) Date of next scheduled assessment² 	Progressed Progressed
C2	Progression or death after two or more missing assessments	 (1) Date of last adequate assessment² (2) Date of next scheduled assessment² (3) Date of progression (or death) 	Censored Progressed Progressed
D	No progression	(1) Date of last adequate assessment	Censored
E	Treatment discontinuation due to 'Disease progression' without documented progression, i.e. clinical progression based on investigator claim	(1) Ignore clinical progression and follow situations above(2) Date of discontinuation (visit date at which clinical progression was determined)	As per above situations Progressed
F	New anticancer therapy given	 (1) Ignore the new anticancer therapy and follow situations above (ITT approach) (2) Date of last adequate assessment prior to new anticancer therapy (3) Date of secondary anti-cancer therapy (4) Date of secondary anti-cancer therapy 	As per above situations Censored Censored Event

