enrollment, allowing for the +1 week visit window for tumor assessments. Patients with only non-measurable disease at baseline will be part of the analysis and will be included in the numerator only if they achieve a complete response or have a 'Non-CR/Non-PD' response 23 weeks or more after start of study treatment. CBR will be calculated using the mFAS based on the investigators' tumor assessments.

Duration of response

Duration of response (DOR) only applies to patients whose best overall response is complete response (CR) or partial response (PR) according to RECIST 1.1 based on local investigators review of tumor assessment data. The start date is the date of first documented response of CR or PR (i.e., the start date of response, not the date when response was confirmed), and the end date is defined as the date of the first documented progression or death due to underlying cancer. Patients continuing without progression or death due to underlying cancer will be censored at the date of their last adequate tumor assessment using the censoring rule described for PFS analysis (options A(1), C2(1), D(1), E(1), F(1-3) and G(1) from Table 3-2 in Appendix 5 of the study protocol).

Overall Survival

OS is defined as the time from date of start treatment to date of death due to any cause. If a patient is not known to have died, then OS will be censored at the date of last known date patient alive.

PFS after next-line of treatment (PFS2)

PFS2 is defined as time from date of start of treatment to the first documented disease progression (clinical or radiologic) on next-line therapy or death from any cause, whichever occurs first. The first documented progression on next-line treatment will be based on investigator assessment of PD (i.e. as captured on the anti-neoplastic therapy after treatment discontinuation CRF page).

1. Next-line therapy is defined as the first new (systemic) anti-neoplastic therapy initiated after discontinuation of study treatment regardless of EoT reason. Drugs given as part of the same regimen should be grouped as one line (i.e. part of the next-line therapy). In addition, continuation of the study treatment after the initial radiologic disease progression will not be considered as next-line therapy.
2. PFS2 will be censored if no PFS2 event (progression or death) is observed during next-line therapy before the analysis cut-off date; the censoring date will be the last contact date.

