New anticancer therapy given prior to protocol defined progression	Ignore the new anticancer therapy and follow situations above	As per above situations
Death before first PD assessment	Date of death	Progressed

ORR

Patients with unknown or missing best overall response (BOR) will be counted as failures. If there is no baseline tumor assessment, all post-baseline overall lesion responses are expected to be 'Unknown'. If no valid post-baseline tumor assessments are available, the best overall response must be "Unknown" unless progression is reported. For the computation of ORR, these patients will be included in the mFAS and will be counted as 'failures'.

PFS 2

For PFS2, refer to [Table 2-6](#) for censoring and event date options and outcomes.

Table 2-6 Outcome and event/censor dates for PFS2 analysis

Situation	Event/Censoring Date	Outcome
No baseline assessment	Date of start of treatment	Censored
Progression or death during the next-line therapy	Date of progression (or death)	Event
Death prior to initiation of next-line therapy	Date of death	Event
No progression (or death) during the next-line therapy and no second new anti-neoplastic therapy is initiated	Last contact date	Censored
No progression (or death) during the next-line anticancer therapy and a second new anti-neoplastic therapy is initiated	End date of the next-line therapy	Censored
No next-line therapy initiated with patient known to be alive	Last contact date	Censored

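### SAP 2.7.2 plans the Kaplan-Meier analysis and median for time to response instead of duration of response, and SAP 2.7.1 cites three incompatible censoring options for DOR

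*SAP*

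**What the plan says.** All SAP references are to Amendment 4, to which the extension-phase SAP defers for the main analyses.

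**Method for DOR.** Protocol 10.5.1.5 states: "DOR will be summarized using Kaplan-Meier estimates in patients with confirmed CR or PR within each cohort". SAP 2.7.2, under Duration of Response, says that DOR (printed as DOOR) is listed and summarized for confirmed responders in the mFAS. It then continues: "The distribution of time to response will be estimated using the Kaplan-Meier method and the median time to response will be presented", with a 95% confidence interval, provided enough responses are seen. It adds: "A responders-only analysis will also be performed in this case".

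**Censoring for DOR.** SAP 2.7.1 censors responders without an event at their last adequate tumor assessment. It says this is the rule used for PFS and cites "options A(1), C2(1), D(1), E(1), F(1-3) and G(1) from Table 3-2 in Appendix 5 of the study protocol". For PFS, SAP Table 2-5 handles new anticancer therapy in one way: "Ignore the new anticancer therapy and follow situations above". Protocol 10.5.1.1 says the same for PFS.

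**Related summary text.** Protocol Table 3-1 and SAP Table 1-1 end DOR at progression or death without saying which deaths count, and they end OS at death or loss to follow-up. Protocol 10.5.1.6 analyses OS in the FAS. SAP 2.7.2 uses the mFAS, which Protocol 10.1.1 names as the primary population for efficacy.

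**The concern.** A programmer working from SAP 2.7.2 would produce a Kaplan-Meier curve and median for a quantity that is in neither objectives table, and would find no estimator for the endpoint that is.

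The sentence about a responders-only analysis adds to the problem. DOR exists only in responders, so an additional responders-only analysis implies that the main one covers all patients. That is the all-patient time-to-response method of Protocol Appendix 5, section 3.2.7, where "patients who did not achieve a response (which may have to be a confirmed response) will be censored using one of the following options". The SAP does not say which option would apply to whom.

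The censoring citation is a separate fault. F(1), F(2) and F(3) are alternatives for the same situation, so one analysis can use only one of them. Appendix 5, section 3.2.10, asks for the primary and sensitivity choices to be specified and for new therapy to be handled in detail. The SAP labels none of the three. In an open-label, non-comparative study, this choice should not be left until the data are in hand.

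**Working it through.** The documents give no planned figure for DOR, so there is none to reproduce. The check compares the passages and then sizes the effect under stated assumptions.

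**1. Which quantity gets the Kaplan-Meier analysis**

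| Place | What it provides |
|---|---|
| Protocol Table 3-1, SAP Table 1-1 | DOR listed as secondary; time to response not listed |
| Protocol 10.5.1.5 | Kaplan-Meier of DOR in confirmed responders |
| SAP 2.7.1 | Start, end and censoring of DOR |
| SAP 2.7.2 | DOR listed and summarized; Kaplan-Meier, median and CI for time to response |
| SAP 5.4.1 | Generic Kaplan-Meier text, no endpoint named |
| SAP section 4 | Changes from protocol: COVID-19 items only |

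The SAP therefore departs from the protocol without declaring it.

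To see what the written analysis would show, take the response rate from the earlier alpelisib plus fulvestrant study (Protocol 1.2.5.2) as an assumption: "Best overall response (BOR) achieved was confirmed PR for 13 (26.5%) patients".

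- Responders per cohort: 0.265 × 112 = 29.7, about 30.
- All-patient time to response, with progressed non-responders censored at maximum follow-up: these patients stay in the risk set throughout, so the cumulative curve levels off near 26.5%. It does not reach 50%, so there is no median.
- Responders only: the first scheduled scan is at 84 / 30.4375 = 2.76 months. The estimate is tied to the scan calendar and says nothing about how long responses last.

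**2. Whether F(1-3) can be one rule**

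Table 3-2 of Appendix 5 gives, for new anticancer therapy:

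- F(1): ignore the new therapy.
- F(2): censor at "Date of last adequate assessment prior to new anticancer therapy".
- F(3): censor at the start of the new therapy.

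Take one hypothetical responder with scans on days 85, 169, 253 and 337, first response on day 85, new therapy on day 200 and progression on day 337. Duration = end − start + 1.

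| Option | Days | Months | Status |
|---|---|---|---|
| F(1) | 337 − 85 + 1 = 253 | 8.31 | event |
| F(2) | 169 − 85 + 1 = 85 | 2.79 | censored |
| F(3) | 200 − 85 + 1 = 116 | 3.81 | censored |

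One patient gets three different results. F(3) also conflicts with the SAP sentence that cites it, because that sentence censors at the last adequate assessment.

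**3. Size across a cohort**

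Assumptions:

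- DOR is exponential with median 9.1 months. This is the median PFS in Protocol 1.2.5.2, used only as a scale.
- Progression is dated at the next 12-weekly scan.
- A share *s* of responders starts new therapy between the last clean scan and the scan that shows progression. No source gives *s*, so a range is shown.

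Probability of passing one scan interval without progression: q = exp(−ln 2 × 2.76 / 9.1) = 0.8104.

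Under F(1), the estimate at 12.4 months, after four scans, is q⁴ = 0.431.

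Under F(2) or F(3), a share *s* of those about to progress leaves the risk set before the scan. The factor per scan becomes q / [1 − s(1 − q)], raised to the fourth power:

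| s | Factor per scan | At 12.4 months | Kaplan-Meier median |
|---|---|---|---|
| F(1) | 0.8104 | 43.1% | 11.04 months |
| 5% | 0.8182 | 44.8% | 11.04 months |
| 10% | 0.8261 | 46.6% | 11.04 months |
| 20% | 0.8424 | 50.3% | 13.80 months |
| 30% | 0.8593 | 54.5% | 13.80 months |

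The medians fall on scan dates: 4 × 2.76 = 11.04 and 5 × 2.76 = 13.80 months.

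**The case against.** **The slip is recognisable.** The heading is Duration of Response, the paragraph already misprints DOR, SAP 2.7.1 defines DOR as a time-to-event variable, and the protocol states the method. It was probably a drafting error, not a decision to drop the analysis. That stands as an account of intent. It does not change what the SAP instructs.

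**The all-patient reading is an inference.** The preceding sentence is restricted to confirmed responders, and Appendix 5 does offer rules for censoring non-responders. This is fair: the result of a median not reached applies only under that reading. On the responders-only reading, the median is still a time to response.

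**The context points to F(1).** The same sentence refers to the PFS rule, option (1) is the Table 3-2 default, and F(1-3) may have meant a primary rule plus sensitivity analyses, or only the exclusion of F(4). All of this is plausible and supports F(1) as the correction. The SAP says none of it.

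**The size estimate is soft.**

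- F(2) and F(3) agree by construction in this model, because new therapy starts only within the last scan interval.
- The protocol works against high values of *s*: it strongly recommends a scan before switching therapy, asks for prompt imaging on suspected progression, and asks for an end-of-treatment scan if the last is over 30 days old.
- The median moves at 20% only because the curve sits at 50.3%, just above one half.
- With about 30 responders, the standard error at 12.4 months is √(0.431 × 0.569 / 30) = 0.090, a 95% half-width of about 18 points. Every shift shown is smaller than that.

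These limits stand. However, the shift from the choice of rule is systematic, whereas the sampling error is random, and it costs nothing to avoid.

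**Conclusion.** The concern holds on both parts. As written, SAP 2.7.2 assigns the time-to-event analysis to an unlisted quantity and gives DOR no estimator, contrary to Protocol 10.5.1.5. SAP 2.7.1 cites three rules where only one can apply, and the PFS rule it invokes is F(1).

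The first fault would put the wrong quantity in the report for a named secondary endpoint. The second would move the 12.4-month DOR estimate by 1.7 to 11.4 percentage points (44.8 − 43.1 and 54.5 − 43.1), and the median by nothing or by one scan interval. Those sizes rest on the assumed exponential DOR, the borrowed 9.1-month scale and the unsourced 5% to 30% range.

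DOR is descriptive here, so the primary test, its alpha and its power are unaffected. The DOR and OS wording in the summary tables and the OS population mismatch are real but minor. The changes should be made.

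**What to change.** - **SAP 2.7.2:** replace time to response with duration of response, estimated by Kaplan-Meier with median and 95% CI among confirmed responders in the mFAS, by cohort. If time to response is also wanted, name it as an additional descriptive summary and state its population and censoring rule.
- **SAP 2.7.1:** replace F(1-3) with F(1), to match PFS. Label any other F option a sensitivity analysis.
- **Protocol Table 3-1 and SAP Table 1-1:** state that DOR ends at progression or death due to underlying cancer, as in Protocol 10.5.1.5 and SAP 2.7.1. An any-cause version can be a sensitivity analysis. Remove loss to follow-up as an end point of OS, because the operative text censors there.
- **OS population:** report the FAS as in Protocol 10.5.1.6 with the mFAS alongside, or list the change to mFAS in SAP section 4.

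The cost is a few words in the SAP and the two summary tables, plus minor programming. No new data, visits or patients are needed.

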2.7.3 Handling of missing values/censoring/discontinuations

PFS

PFS will be censored at the date of the last adequate tumor assessment if no PFS event is observed prior to the analysis cut-off date.

PFS events documented after the initiation of new anti-neoplastic therapy (i.e. RECIST 1.1 documented disease progression or death) will be considered for the primary analysis provided tumor assessments continue after initiation of new cancer therapy.

The date of last adequate tumor assessment is the date of the last tumor assessment with overall lesion response of CR, PR or SD before an event or a censoring reason occurred. In this case the last tumor evaluation date at that assessment will be used. If no post-baseline assessments are available (before an event or a censoring reason occurred) then the date of randomization/start date of treatment will be used.

In particular, PFS will be censored at the last adequate tumor assessment if one of the following occurs: absence of event, the event occurred after two or more missing tumor assessments. The term “missing adequate tumor assessment” is defined as a tumor assessment (TA) not performed or tumor assessment with overall lesion response of “UNK”. The rule to determine number of missing TAs is based on the time interval between the date of last adequate tumor assessment and the date of an event. If the interval is greater than twice the protocol-specified interval between the TAs and 2 times the protocol-allowed time window around assessments, then the number of missing assessments will be 2 or more.

Refer to [Table 2-5](#) for censoring and event date options and outcomes for PFS.

Table 2-5 Outcome and event/censor dates for PFS analysis

Situation	Date	Outcome
No baseline assessment	Date of start of treatment	Censored
Progression or death at or before next scheduled Assessment	Date of progression (or death)	Progressed

Situation	Date	Outcome
Progression or death after exactly one missing assessment	Date of progression (or death)	Progressed
Progression or death after two or more missing assessments	Date of last adequate assessment prior to missed assessment	Censored
No progression (or death)	Date of last adequate assessment	Censored
Treatment discontinuation due to 'Disease progression' without documented progression, i.e. clinical progression based on investigator claim	Date of last adequate assessment	Censored
New anticancer therapy given prior to protocol defined progression	Ignore the new anticancer therapy and follow situations above	As per above situations
Death before first PD assessment	Date of death	Progressed

ORR

Patients with unknown or missing best overall response (BOR) will be counted as failures. If there is no baseline tumor assessment, all post-baseline overall lesion responses are expected to be 'Unknown'. If no valid post-baseline tumor assessments are available, the best overall response must be "Unknown" unless progression is reported. For the computation of ORR, these patients will be included in the mFAS and will be counted as 'failures'.

PFS 2

For PFS2, refer to [Table 2-6](#) for censoring and event date options and outcomes.

Table 2-6 Outcome and event/censor dates for PFS2 analysis

Situation	Event/Censoring Date	Outcome
No baseline assessment	Date of start of treatment	Censored
Progression or death during the next-line therapy	Date of progression (or death)	Event
Death prior to initiation of next-line therapy	Date of death	Event
No progression (or death) during the next-line therapy and no second new anti-neoplastic therapy is initiated	Last contact date	Censored
No progression (or death) during the next-line anticancer therapy and a second new anti-neoplastic therapy is initiated	End date of the next-line therapy	Censored
No next-line therapy initiated with patient known to be alive	Last contact date	Censored

